#### **Delta Adjustment Imputation Methods**

This MNAR sensitivity analysis is to departure from MAR assumption by progressively increasing the delta until conclusion from the primary analysis is overturned. The delta is 0%, 10%, 20%, 30%, ..., 100% of the expected treatment difference of 3 points and/or the observed treatment difference between CT-152 and sham from the primary analysis of MMRM model until conclusion of the primary analysis is overturned. When delta=0 it is MAR. When delta > 0 it is MNAR.

- Using Monte Carlo Markov Chain (MCMC) methodology from PROC MI to impute the intermittent missing data to a monotone missing pattern
- 2) Using a standard MAR-based multiple imputation approach from PROC MI to impute the monotone missingness data
- 3) For patients in the treated group and with a dropout reason of AE or LOE or subject withdrew consent, a delta will be added for all the values after the dropout time
- Using analysis of covariance (ANCOVA) model to analyze the completed data through multiple imputation.
- 5) Obtaining the overall results using PROC MIANALYZE.

#### **Placebo Based Imputation Methods**

Similar to "Standard" multiple imputations, except parameters for imputation model obtained from only the placebo (sham) group. Missing data for both sham and CT-152 group are imputed based on the imputation model derived from sham data. If CT-152 improved outcomes prior to dropout, this benefit is carried into subsequent imputed values, but will diminish over time in accordance with the correlation structure.

In addition, model based MNAR methods such as the shared parameter model (Wu and Baily, 1989) and random coefficient pattern mixture model (Hedeker D, Gibbons RD, 1997) will be also performed.

#### **LOCF and OC Analyses**

Change from baseline for the MADRS total score will be evaluated using ANCOVA with baseline value as covariate and treatment and, in LOCF analyses, trial site as main effects. For the OC analyses, trial site will not be included in the model.

# 8.1.3.2 Per Protocol Analyses

Per-protocol analyses will be conducted as sensitivity analyses to the primary efficacy endpoint and key secondary endpoint described in Section 8.2 on the PP analysis set.

# 8.1.3.3 Sensitivity Analyses for Violation of Normality Assumption

The primary endpoint MMRM analysis is a maximum likelihood method that relies on normality assumption. Residual analyses will be carried out to examine model assumption.

In the case of gross violations of the normality assumptions, nonparametric van Elteren test (van Elteren, 1960) will be performed to compare treatment effect at Week 6 on both LOCF dataset and Multiple Imputation (MI) data. The van Elteren test is a generalized CMH procedure useful for stratified continuous data in non-normal setting. It belongs to a general family of Mantel-Haenszel mean score tests. The test is performed via SAS procedure PROC FREQ, by including CMH2 and SCORES=MODRIDIT options in the TABLE statement. The stratification factor is trial site.

In addition, other methods that are robust to distributional assumption will also be performed to provide different views on the primary efficacy result, these include generalized estimating equations (GEE), weighted GEE (WGEE), and MI-robust regression.

For MI-van Elteren test and MI-robust regression, imputation datasets will be generated with SAS MI procedure, each dataset will be analyzed, then an overall estimate is derived with SAS MIANALYZE procedure.

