# 4 Sample Size and Power Justification

The primary efficacy endpoint is the change from baseline at Week6 in Montgomery-Asberg Depression Rating Scale (MADRS) total Score. The trial will compare CT-152 to sham, randomized at a ratio of 1:1, with an overall alpha of 0.05 for the primary efficacy endpoint.

The initial sample size is calculated to detect a 3-point difference between CT-152+ADT and sham+ADT in the change from baseline in MADRS total score with 85% power at a 2-sided  $\alpha$  = 0.05 level, assuming a common standard deviation of 9. The resulting sample size is 324 evaluable subjects in total (162 subjects in each arm). To compensate for subjects that fail to have evaluable assessments of MADRS total score in the full analysis set (FAS) Sample (estimated at up to 10% of all subjects), a total of 360 subjects (180 subjects in each arm) will be randomized in this trial.

Due to the limitations of applying assumptions on the treatment effect size, and in order to ensure adequate power of the trial, an unblinded interim analysis (IA) will be conducted by a Data Monitoring Committee (DMC) on when approximately the first 180 randomized subjects had an opportunity to complete the Week 6 visit. The final sample size could be increased to 540 subjects (270 subjects in each arm) as per recommendation of the DMC. Using the O'Brien-Fleming spending function, an alpha level of 0.003 (2-sided) is allocated to this interim analysis. The alpha level left for the final analysis is 0.049 (2-sided). The power and sample size were obtained using the PASS 14 (2015) statistical computing software.

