# 8.1.1 Primary Efficacy Analysis

The null hypothesis of the statistical test comparing CT-152+ADT and sham+ADT, based on the primary efficacy endpoint, is that the change in MADRS total score using CT-152+ADT is equal to the change in MADRS using the sham+ADT.

 $H_0$ :  $\Delta \mu_{MADRS\ CT-152+ADT} = \Delta \mu_{MADRS\ sham+ADT}$ 

Ha:  $\Delta \mu$  madrs ct-152+adt  $\neq \Delta \mu$  madrs sham+adt

The primary analysis will be conducted on the change from baseline in MADRS total score to the final on-therapy evaluation (Week 6) based on the FAS Sample adjusted for the baseline MADRS total score.

for efficacy, or if the p-value of the statistical comparison based on the primary efficacy endpoint at final is < 0.049.

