## 8.1.1.2 Primary Analysis Method

The primary analysis will utilize a MMRM with an unstructured (UN) variance covariance matrix in which the change from baseline in MADRS total score at scheduled treatment period visits (Weeks 2, 4, and 6) will be the dependent variable based on the OC data set on FAS Sample. The model will include fixed class effect terms for treatment, visit, treatment by visit interaction, and site to assess heterogeneity of treatment effects. This model will also include an interaction term of visit by baseline MADRS total score as a covariate. The primary comparison between the CT-152+ADT or sham+ADT at Week 6 will be estimated as the difference between least squares means utilizing the computing software SAS procedure PROC MIXED.

The mathematical formula for the MMRM model is as follows:

$$\mathbf{y} = \mathbf{X}\boldsymbol{\beta} + Z\mathbf{u} + \epsilon$$

Where

y denotes the observed vector of change from baseline to Week 6 in MADRS total score;

X is the known matrix for the fixed effects and covariate;

 $\beta$  is an unknown fixed-effect parameter vector;

Z is the known matrix for the random effect of subject;

u is an unknown vector of random effect of subject with mean  $\mathbf{0}$  and variance-covariance matrix  $\mathbf{G}$  (unstructured covariance matrix);

 $\epsilon$  is an unknown vector of random errors with mean 0 and variance **R**.

In case there is a convergence problem with the MMRM model with the unstructured variance-covariance matrix, the following structures other than unstructured will be used in order of 1) heterogeneous toeplitz (TOEPH), 2) heterogeneous autoregressive of order 1 (ARH1), and 3) heterogeneous compound symmetry (CSH). The first (co)variance structure converging to the best fit will be used as the primary analysis. If a structured covariance has to be used, the "sandwich" estimator of the standard error of the fixed effects parameters will be used in order to deal with possible model misspecification of the covariance matrix.

Small trial sites will be defined as trial sites that do not have at least one evaluable subject (evaluable with regard to the primary efficacy variable) in each treatment arm. All small trial sites will be pooled to form "pseudo sites"

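### The one rank test named for gross non-normality (SAP 8.1.3.3) is stratified by site but leaves out baseline MADRS, which costs some precision if baseline predicts change

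*SAP*

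**What the plan says.** SAP 8.1.1 states that the primary analysis is "based on the FAS Sample adjusted for the baseline MADRS total score". SAP 8.1.1.2 carries this into the MMRM: "This model will also include an interaction term of visit by baseline MADRS total score as a covariate". The SAS code in 8.1.2 contains the same term. Two sensitivity analyses also keep baseline MADRS as a covariate: the LOCF and OC ANCOVA in 8.1.3.1 and the Randomized Sample analysis in 8.1.3.4.

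SAP 8.1.3.3 covers non-normal residuals: "In the case of gross violations of the normality assumptions, nonparametric van Elteren test" will compare the arms at Week 6 on LOCF and MI data, through PROC FREQ with CMH2 and modified ridit scores. On strata it says only: "The stratification factor is trial site". No baseline term appears. The section justifies the method as suited to stratified continuous data that are not normal. It then adds GEE, weighted GEE and MI-robust regression without listing their covariates.

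The SAP addendum of 16 November 2022 does not change 8.1.3.3.

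**The concern.** The van Elteren test would be read when the normality behind the MMRM is in doubt. As specified, it differs from the MMRM in three ways: it uses ranks, it handles missing data by LOCF or MI, and it drops baseline. The LOCF ANCOVA helps to isolate the effect of LOCF. No fully specified analysis is both rank-based and baseline-adjusted, so the effect of ranking cannot be cleanly separated from the effect of dropping the covariate. If the van Elteren result disagreed with the MMRM, then non-normality, lower precision and a chance baseline imbalance would all be possible explanations.

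Missing baselines do not explain the omission. SAP 5.1 requires a baseline MADRS for membership of the FAS, and SAP 8 puts the efficacy analyses on the FAS. Nor does the change score settle the matter, because subtracting baseline does not remove its correlation with the change.

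**Working it through.** **1. The plan's own figure.** SAP 4: "The initial sample size is calculated to detect a 3-point difference between CT-152+ADT and sham+ADT", with SD 9, 85% power and two-sided alpha 0.05. Per arm, n = 2(1.960 + 1.036)² × 9² / 3² = 161.6, rounded up to 162, so 324 in total. Then 324 / 0.90 = 360 randomized. Both figures reproduce, and neither rests on the van Elteren test. The plan states no power for that test.

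**2. Precision lost by omitting baseline.** Let rho be the correlation of baseline with change. The variance ratio, unadjusted to adjusted, is 1 / (1 − rho²).

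| rho | variance ratio | SE larger by |
|---|---|---|
| 0 | 1.00 | 0% |
| 0.3 | 1.10 | 5% |
| 0.5 | 1.33 | 15% |

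**3. What rho might be.** The documents give neither rho nor a baseline SD. Assume baseline SD b of 5 to 7, Week 6 SD of 9, and baseline-to-Week 6 correlation r of 0.3 to 0.5. Then R² of change on baseline = (9r − b)² / (81 + b² − 18rb).

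- Lowest, b = 5 and r = 0.5: (4.5 − 5)² / (81 + 25 − 45) = 0.25 / 61 = 0.004.
- Highest, b = 7 and r = 0.3: (2.7 − 7)² / (81 + 49 − 37.8) = 18.49 / 92.2 = 0.20.

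So R² runs from 0.004 to 0.20, and the size of rho from about 0.06 to 0.45 (square roots). A rho of 0.5 (R² = 0.25) lies just outside this range. It would arise with equal SDs of 9 and r = 0.5: (4.5 − 9)² / (81 + 81 − 81) = 20.25 / 81.

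**4. Simulated power.** Each setting had 1,500 runs with 324 subjects, 50 sites of uneven size, a 3-point effect, SD of change 9, two-sided 0.049 and one Week 6 outcome. The adjusted test is van Elteren by site on residuals from a regression of change on baseline.

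| Errors | rho | van Elteren, site only | van Elteren, baseline-adjusted | ANCOVA, site + baseline |
|---|---|---|---|---|
| t, 3 df | 0 | 0.962 | 0.964 | 0.846 |
| t, 3 df | 0.3 | 0.948 | 0.976 | 0.877 |
| t, 3 df | 0.5 | 0.899 | 0.992 | 0.922 |
| Exponential | 0 | 0.986 | 0.985 | 0.838 |
| Exponential | 0.3 | 0.950 | 0.990 | 0.872 |
| Exponential | 0.5 | 0.895 | 0.995 | 0.921 |

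The gains from adjusting the rank test are:
- rho 0.3: 0.976 − 0.948 = 2.8 points and 0.990 − 0.950 = 4.0 points.
- rho 0.5: 0.992 − 0.899 = 9.3 points and 0.995 − 0.895 = 10.0 points.
- rho 0: no difference beyond simulation error.

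Ranking both change and baseline before the regression gave essentially the same power, 0.975 to 0.993.

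**5. Validity as written.** With no treatment effect and rho 0.3, the site-only test rejected in 0.043 to 0.045 of runs at the 0.049 level.

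**The case against.** The strongest reply is that nothing turns on this test. It is one of several conditional sensitivity analyses and has no decision rule or alpha of its own. A van Elteren test takes strata rather than a continuous covariate, so the omission comes with the named method, and the SAP does say why a rank test is used. Under the non-normality that would trigger it, the site-only rank test is more powerful than baseline-adjusted ANCOVA at rho 0 and 0.3, and only 2 to 3 points below it at rho 0.5. All of this stands, and it makes the point minor. It supports using a rank test, though, not leaving baseline out of one. The same table shows the adjusted rank test at least matching the unadjusted one to within simulation error, and clearly ahead once baseline predicts change.

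The reply can add that the van Elteren result is not read alone, since the LOCF ANCOVA and the robust models sit beside it. That is partly right. The ANCOVA is not rank-based, and the covariates of the robust models are not stated.

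A further objection is that least-squares regression of raw change before ranking brings in a tail-sensitive step exactly where tails are the worry. That is fair, and it is met by ranking change as well as baseline.

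A reader might infer that this test takes over as the primary analysis when normality fails, or that the trial's power is at risk. The documents do not support either reading. SAP 8.1.3.3 is a sensitivity section, nothing in it displaces the MMRM, and SAP 8.1.1 ties success to the primary comparison at p < 0.049.

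**Conclusion.** The point holds as a minor, inexpensive improvement. The one named rank test omits a covariate that the primary model and the LOCF ANCOVA use, that every FAS subject has, and whose omission is not explained. The consequence is lower precision and a less clean comparison with the MMRM. It is not bias, an inflated type I error or an effect on sample size.

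The size depends on a correlation the plan does not give. Over the assumed range (R² of 0.004 to 0.20) the gain runs from almost nothing to several power points. The 9 to 10 points at rho 0.5 lie just beyond that range. The simulation also assumes the error shapes and site sizes, and reads SD 9 as the SD of unadjusted change, which SAP 4 does not specify.

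**What to change.** In SAP 8.1.3.3, specify a stratified rank ANCOVA as the rank test:

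- Rank the Week 6 change and baseline MADRS.
- Regress ranked change on ranked baseline, without treatment in the model.
- Run the same CMH2 test with modified ridit scores on the residuals, stratified by pooled site, for both LOCF and MI data.

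Keep the plain van Elteren test as a secondary line. State in the same section that the GEE, weighted GEE and MI-robust regression include baseline MADRS. Make the change before unblinding so that the choice cannot depend on the results.

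The cost is a sentence or two in the SAP and a few lines of SAS, with no new data. The downside is one extra modelling step before the rank test.

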## 8.1.3.4 Sensitivity Analyses for Randomized Sample

Primary analysis will be performed on Randomized Sample with multiple imputation method to impute the missing MADRS total scores, including subjects who are excluded from FAS Sample, that is, those who do not complete the baseline and any postbaseline MADRS assessment. The detailed steps of the method are described below:

1) Using MCMC methodology from PROC MI to impute the intermittent missing data to a monotone missing pattern, with 100 multiple imputations

- Using a standard MAR-based multiple imputation approach from PROC MI to impute the monotone missingness data
- 3) Using ANCOVA model to analyze the completed data through multiple imputation for the primary efficacy endpoint of change from baseline to Week 6 in MADRS total score. Fixed variables in the model are treatment, treatment by visit and pooled center, with baseline MADRS by visit as covariate
- 4) Obtaining the overall results using PROC MIANALYZE.

#### 8.1.4 Subgroup Analyses

Subgroup analyses of change from baseline in MADRS total score to every scheduled visit in the treatment period will be performed by the following factors:

- Sex (Based on the biological status)
- Race (White and All Other Races)
- Age group (Age < 55 and Age  $\ge 55$ )
- Cannabis use (subjects reporting current cannabis use at screening or with positive THC test results at screening)

All subgroup analyses will be conducted using the same MMRM analysis as for the primary efficacy analysis except that the fixed class effect term for trial center will not be included in the model.

Interaction effects of treatment-by-subgroup will be assessed at Week 6 for the subgroups identified in the previous paragraph. MMRM analyses will be performed by adding addition of terms for subgroup-by week and treatment-by-subgroup-by-week. These treatment-by-subgroup interaction analyses will be presented in statistical documentation.

#### 8.2 Key Secondary Efficacy Endpoint

The key secondary efficacy endpoint is the change from baseline to Week 6 in the GAD-7 total score. It will be analyzed using the same method (MMRM) as in the primary analysis with a replacement of the interaction term of visit by baseline GAD-7 total score as a covariate. The null hypothesis of the statistical test comparing CT-152+ADT and sham+ADT, based on the key secondary efficacy endpoint, is that the change from baseline to Week 6 in the GAD-7 total score using CT-152+ADT is equal to the change from baseline to Week 6 in the GAD-7 total score using sham+ADT.

$$H_0$$
:  $\Delta \mu_{GAD-7 CT-152+ADT} = \Delta \mu_{GAD-7 sham+ADT}$ 

$$H_A$$
:  $\Delta \mu_{GAD-7 CT-152+ADT} \neq \Delta \mu_{GAD-7 sham+ADT}$ 

where  $\Delta\mu_{\text{GAD-7 CT-152+ADT}}$  and  $\Delta\mu_{\text{GAD-7 sham+ADT}}$  are the change from baseline to Week 6 in the GAD-7 total score in CT-152+ADT and sham+ADT treatment groups, separately.

In order to control the overall type I error rate, the statistical tests based on the primary efficacy endpoint and the key secondary efficacy endpoint will be done using a hierarchical approach. If the primary efficacy analysis for the MADRS total score yields a statistically significant result with the pre-specified alpha level at the IA or the final analysis (if the trial does not stop at the IA) for the comparison of CT-152 and sham, then the corresponding comparison for the key secondary efficacy endpoint (GAD-7 total score) will be tested using the same alpha-spending as that of the primary endpoint.

Should the primary outcome not achieve statistical significance in the final analysis, the key secondary endpoint will be examined as an other efficacy endpoint.

# 8.2.1 Efficacy Endpoints for Assessment for Durability

The durability of effect of CT-152 will be assessed based on MADRS total score and GAD-7 total score.

It will include 3 MADRS assessments at Weeks 6, 8, and 10. In addition to demonstrating an with statistical significance, durability will be demonstrated by a point estimate of the difference in change from baseline at Weeks 8 and 10 when comparing CT-152 and sham. Such point estimates will be provided using the same MMRM model in the primary efficacy analysis with change from baseline in MADRS total score at Week 8 and 10 in the extension period as the dependent variable.

Durability based on GAD-7 will also include 3 assessments, at Weeks 6, 8, and 10, demonstrating a numerically larger improvement on point estimate of the difference in change from baseline in GAD-7 total score at Weeks 8 and 10 in CT-152 compared to sham. Such point estimates will be provided using the same MMRM model in the key secondary efficacy analysis with change from baseline in GAD total score at Week 8 and 10 in the extension period as the dependent variable.

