Due to the limitations of applying assumptions on the treatment effect size, and in order to ensure adequate power of the trial, an unblinded interim analysis will be conducted by

a DMC. The final sample size could be increased to 540 subjects (270 subjects in each arm) as per recommendation of the DMC. Using the O'Brien-Fleming spending function, a significance level of 0.003 (2-sided) is allocated to this interim analysis. The corresponding final significance level is 0.049 (2-sided).

The null hypothesis of the statistical test comparing CT-152+ADT and sham+ADT, based on the primary efficacy endpoint, is that the change in MADRS using CT-152+ADT is equal to the change in MADRS using the sham+ADT.

The primary analysis will be conducted on the change from baseline in MADRS total score to the final on-therapy evaluation (Week 6) based on the FAS sample adjusted for the baseline MADRS total score.

CCI
. In this trial, we plan to detect a 3-point difference on the primary
efficacy endpoint between the treatment groups. CCI
This trial is considered positive if the trial will be stopped at the
interim analysis for efficacy, or if the p-value of the statistical comparison based on the
primary efficacy endpoint at final is < 0.049 .

The primary analysis will utilize mixed model repeated measurements (MMRM) with treatment, visit, treatment by visit interaction, and site as fixed effects to assess heterogeneity of treatment effects. The key secondary efficacy endpoint and other efficacy endpoints will be analyzed based on the FAS as described for the primary analysis.

The null hypothesis of the statistical test comparing CT-152+ADT and sham+ADT, based on the key secondary efficacy endpoint, is that the change from baseline to Week 6 in the GAD-7 total score using CT-152+ADT is equal to the change from baseline to Week 6 in the GAD-7 total score using sham+ADT.

The key secondary efficacy endpoint will be analyzed using the same method (MMRM) as in the primary analysis with a replacement of the interaction term of visit by baseline GAD-7 total score as a covariate.

The durability of effect of CT-152 will be assessed based on MADRS total score and GAD-7 total score at Weeks 6, 8 and 10. Change from baseline to Week 8 and 10 in the above assessments will be analyzed using MMRM as described for the primary analysis.

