In this hypothetical strategy, the event of withdrawing CT-152+ADT or sham+ADT is considered missing at random (MAR), and the primary endpoint of the trial could be considered as a combination of the measurements of on-treatment completers at Week 6 and the imputation of the endpoint to Week 6 following the trend in each treatment group using the mixed model repeated measurements (MMRM) method to impute missing data for subjects who withdraw CT-152+ADT or sham+ADT during the trial. All data collected during the trial treatment period will be used for statistical analysis. For the primary efficacy analysis, the treatment effect will be estimated using the MMRM method described in Section 9.4.1.1.2. Under the MAR assumption, MMRM provides an unbiased estimate of treatment effect for the treatment period. Analyses with missing values imputed by multiple imputation under missing not at random (MNAR), and other methods will be performed as sensitivity analyses.

Protocol No. 345-201-00002

9.4.1.1.2 **Primary Analysis Method**

The primary analysis will utilize a MMRM with treatment, visit, treatment by visit interaction, and site as fixed effects to assess heterogeneity of treatment effects. This model will also include an interaction term of visit by baseline MADRS total score as a covariate. Observed data from all planned visits during the 6-week treatment period will be included in the model. An unstructured covariance matrix will be used to model the within subject variance. The primary comparison between the CT-152+ADT or sham+ADT at Week 6 will be estimated as the difference between least squares means utilizing the computing software SAS procedure PROC MIXED.

The mathematical formula for the MMRM model is as follows:

$$y = X\beta + Zu + \epsilon$$

Where

y denotes the observed vector of change from baseline to Week 6 in MADRS total score;

X is the known matrix for the fixed effects and covariate;

 β is an unknown fixed-effect parameter vector;

Z is the known matrix for the random effect of subject;

u is an unknown vector of random effect of subject with mean 0 and variance-covariance matrix **G** (unstructured covariance matrix);

 ϵ is an unknown vector of random errors with mean 0 and variance **R**.

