9.4.1.2.2 Efficacy Endpoints for Assessment of Durability

The durability of effect of CT-152 will be assessed based on MADRS total score and GAD-7 total score.

Protocol No. 345-201-00002

It will include 3 MADRS assessments at Weeks 6, 8, and 10. In addition to demonstrating an MCID group difference of 1.6 to 1.9 at Week 6 with statistical significance, durability will be demonstrated by a point estimate of the difference in change from baseline at Weeks 8 and 10 above 1.6, when comparing CT-152 and sham. Such point estimates will be provided using the same MMRM model in the primary efficacy analysis with change from baseline in MADRS total score at Week 8 and 10 as the dependent variable.

Durability based on GAD-7 will also include 3 assessments, at Weeks 6, 8, and 10, demonstrating a numerically larger improvement on point estimate of the difference in change from baseline in GAD-7 total score at Weeks 8 and 10 in CT-152 compared to sham. Such point estimates will be provided using the same MMRM model in the key secondary efficacy analysis with change from baseline in GAD total score at Week 8 and 10 as the dependent variable.

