The primary analysis will be performed on the FAS Sample which includes all randomized subjects who receive at least 1 occurrence of either CT-152 or sham use, and have both a baseline and at least one postbaseline assessment of MADRS total score. The primary efficacy analysis will be performed by fitting a mixed model repeated measurements (MMRM) analysis with an unstructured (UN) variance covariance structure, in which the change from baseline in MADRS total score (at Weeks 2, 4, and 6) during treatment period will be the dependent variable based on the OC data set. The model will include fixed class effect terms for treatment, visit, treatment by visit interaction, and site to assess heterogeneity of treatment effects. The model will also include an interaction term of visit by baseline MADRS total score as a covariate. The primary comparison between the CT-152+ADT and Sham +ADT at Week 6 will be estimated as the difference between Least Squares (LS) means utilizing the computing software SAS procedure PROC MIXED. In case there is a convergence problem with MMRM model with the unstructured (UN) variance covariance matrix, the following structures other than unstructured will be used in order of 1) heterogeneous toeplitz (TOEPH), 2) heterogeneous autoregressive of order 1 (ARH1), and 3) heterogeneous compound symmetry (CSH) and the first (co)variance structure converging to the best fit will be used as the primary analysis. If a structured covariance has to be used, the empirical "sandwich" estimator of the standard error of the fixed effects parameters will be used in order to deal with possible model misspecification of the covariance matrix.

To assess the durability of effect of CT-152, three MADRS assessments at Weeks 6, 8, and 10 will be included.

at Week 6 with statistical significance, durability will be demonstrated by a point estimate of the difference in change from baseline at Weeks 8 and 10 above 1.6, when comparing CT-152 and sham. Such point estimates will be provided using the same MMRM model in the primary efficacy analysis with change from baseline in MADRS total score at Week 8 and 10 as the dependent variable.

This key secondary efficacy endpoint will be analyzed by fitting the same MMRM model as described in the primary analysis with change from baseline in GAD-7 total score (at Weeks 2, 4, and 6) as the dependent variable.

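### As worded, the durability MMRM enters only Weeks 8 and 10, so the Week 2-6 scores of subjects who leave early go unused and the estimates held to 1.6 can be biased

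*SAP*

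**What the plan says.** SAP 8.2.1 obtains the durability estimates from the model of the primary analysis, "with change from baseline in MADRS total score at Week 8 and 10 in the extension period as the dependent variable". IAP 2.2 has "change from baseline in MADRS total score at Week 8 and 10 as the dependent variable", and Protocol 9.4.1.2.2 has a matching sentence. The GAD-7 durability model is worded in the same way.

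The criterion is in Protocol 9.4.1.2.2: "durability will be demonstrated by a point estimate of the difference in change from baseline at Weeks 8 and 10 above 1.6". SAP 8.6 and IAP Table 2.2-2 also require the Week 6, 8 and 10 estimates to exceed 1.6 before the trial may stop early for efficacy.

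For the primary model, SAP 8.1.1.2 states that "the change from baseline in MADRS total score at scheduled treatment period visits (Weeks 2, 4, and 6) will be the dependent variable", and Protocol 9.4.1.1.2 adds: "Observed data from all planned visits during the 6-week treatment period will be included in the model".

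The data rules that matter here are:

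- SAP 5.2 runs MMRM on observed cases without imputation. Even in the LOCF set, Week 6 is not carried to Week 8.
- SAP 5.1 admits a subject to the FAS on one post-baseline MADRS.
- SAP 10.1 assigns all visits, early termination (ET) included, by study day. The Week 8 window opens on Day 49.

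Some text points towards a wider model. SAP 8.2.1 says of the durability assessment: "It will include 3 MADRS assessments at Weeks 6, 8, and 10". IAP 2.2 says "three MADRS assessments at Weeks 6, 8, and 10 will be included". The Protocol synopsis says the Week 8 and 10 changes "will be analyzed using MMRM as described for the primary analysis".

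**The concern.** An MMRM is valid under MAR because the earlier outcomes that predict dropout are in the likelihood. If only Weeks 8 and 10 are entered, a subject last rated before Day 49 contributes nothing, and the model conditions only on baseline, treatment and site. Dropout that is MAR given Weeks 2-6 is then no longer ignorable. The plan's own MAR statement (SAP 8.1.1.1) covers the treatment period only. SAP 8.1.3.1 expects that dropout for adverse events or lack of efficacy may be informative, and SAP 8.1.3 details missing-data sensitivity analyses for the primary endpoint only.

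The durability decision compares two point estimates with a fixed 1.6, without a test or an interval, so any bias passes straight into the conclusion. The same estimates are one condition of the interim efficacy stop.

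**Working it through.** **1. The plan's own figures.** With difference 3, SD 9, two-sided 0.05 and 85% power: n per arm = 2 × (1.960 + 1.036)² × 9²/3² = 161.6, so 162 per arm and 324 in total; 324/0.9 = 360. These reproduce. The standard error of a difference at 162 per arm is 9 × √(2/162) = 1.0.

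**2. Which visits enter.** SAP 8.1.1.2 uses the dependent-variable phrase to list the primary model's visits (Weeks 2, 4, 6). The parallel phrase in SAP 8.2.1 lists Weeks 8 and 10. No text names a model spanning both periods.

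**3. Simulation inputs.** From the plan: SD 9, difference 3, 162 per arm. Assumed, because the documents do not give them:

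- SD of change 6.5/8/9/9/9 at Weeks 2/4/6/8/10.
- Visit correlation 0.75 to the power of the lag, after a -0.3 correlation with baseline.
- Sham mean change -4/-7/-9/-9.5/-10; benefit 1/2/3 at Weeks 2/4/6 and 3.0 at Weeks 8 and 10.
- Half of those leaving between Weeks 6 and 8 have an ET score that falls in the Week 8 window.
- Monotone dropout from Week 2 with logit p = a + b × (last observed change + 7)/8. For MCAR, a = -3.2 and b = 0. For the shared and twofold cases, a = -3.0, with b = 1 in both arms (shared), or 1 in one arm and 0.5 in the other (twofold). For CT-152 only, a = -2.9/-3.2 and b = 1/0 (CT-152/sham). For sham only, a = -3.2 and b = 0/1.

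Estimates are maximum likelihood with treatment and baseline at each visit; site is omitted. There were 4,000 trials per scenario, with a Monte Carlo standard error of about 0.016. Differences are expressed as benefit of CT-152.

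**4. Estimates at Week 8/Week 10 (truth 3.0/3.0).**

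| Dropout | Weeks 8/10 only | Weeks 6/8/10 | Weeks 2-10 |
|---|---|---|---|
| MCAR | 2.99/3.00 | 2.99/3.00 | 2.99/3.00 |
| Shared (19% CT-152, 23% sham missing at Week 10) | 2.88/2.92 | 2.92/2.95 | 3.00/3.01 |
| Twofold, steeper in CT-152 (19%, 19%) | 3.27/3.21 | 3.23/3.17 | 3.00/3.00 |
| Twofold, steeper in sham (17%, 23%) | 2.58/2.69 | 2.68/2.77 | 3.00/3.01 |
| CT-152 only | 3.59/3.45 | 3.46/3.35 | 2.99/3.00 |
| Sham only | 2.43/2.58 | 2.57/2.68 | 2.99/3.01 |

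The two-visit bias is therefore 3.00 - 2.92 = 0.08 to 3.00 - 2.88 = 0.12 (shared), and 3.21 - 3.00 = 0.21 to 3.00 - 2.58 = 0.42 (twofold).

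**5. Range.** Over correlations of 0.6-0.85 and ET capture of 0-50%, the absolute two-visit bias is 0.03-0.21 (shared), 0.12-0.66 (twofold) and 0.21-0.91 (one arm only). The Weeks 2-10 model stays within 0.03. With a = -3.9 (about 8-11% missing), the two-visit model gives 2.94/2.98 (shared) and 3.15/3.11 or 2.81/2.85 (twofold), a bias of 0.02-0.06 and 0.11-0.19.

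**6. A different mechanism.** Here dropout occurs only after Week 6, the adjacent-visit correlation is 0.7 and the true Week 8/10 difference is 1.6. One Week 6-dependent dropout function for both arms, with 10-30% leaving, gives 1.00-1.44 at Week 8 and 1.20-1.49 at Week 10 from the two-visit model, against 1.57-1.62 from Weeks 2-10.

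**7. Chance that both estimates exceed 1.6 (two-visit vs Weeks 2-10), assumptions of step 3.**

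| True Week 8/10 difference | Shared | Steeper in CT-152 | Steeper in sham |
|---|---|---|---|
| 2.0 | 51% vs 55% | 65% vs 56% | 41% vs 55% |
| 1.2 | 21% vs 24% | 33% vs 24% | 15% vs 25% |

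**8. Interim.** With 81 per arm, a true difference of 3.0 and an assumed 25%/50% not yet at Weeks 8/10, the 1.6 condition fails, given p < 0.003, in 8.7% vs 7.4% (MCAR), 10.3% vs 7.4% (shared), 6.7% vs 7.6% (steeper in CT-152) and 12.9% vs 7.5% (steeper in sham).

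**9. MNAR (dropout driven by the missed score; truth 3.0).** Two-visit vs Weeks 2-10: shared 2.80/2.81 vs 2.90/2.89; twofold 3.27/3.26 vs 3.12/3.15 and 2.47/2.50 vs 2.74/2.71. The joint model roughly halves the bias and does not remove it.

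**The case against.** The wording may not be meant as a full list of visits. The plan's formula for the primary model describes the outcome vector as change to Week 6 although Weeks 2 and 4 also enter, and Protocol 9.4.1.2.3 analyses Weeks 2 and 4 with that same multi-visit model. Together with "three MADRS assessments at Weeks 6, 8, and 10 will be included" and "will be analyzed using MMRM as described for the primary analysis", a joint fit is a possible reading. This stands as ambiguity, but no text states such a model. The narrower Weeks 6/8/10 reading is still partly biased, so the result would depend on which reading is programmed.

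The plan sets its hypothetical estimand for Week 6 only. This also stands: the bias is measured against a no-withdrawal target carried forward to Weeks 8 and 10, and the plan does not say that it is.

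The size is not established. At 8-11% missing the bias is modest against a standard error of 1.0, and the larger figures need dropout slopes that differ by arm, which nothing in the documents predicts. Besides MCAR and baseline-only dropout, the bias also vanishes if equal shares of equally ranked subjects leave both arms. These limits stand and are carried into the conclusion.

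Two further points do not answer the concern. The plan asks for end-of-trial procedures from anyone who leaves after Week 6, but raising ET capture to 80% still gave 2.64/2.71 in the twofold case with the steeper slope in sham. SAP Addendum section 4 adds responder and remission analyses at Weeks 8 and 10, which broaden the evidence but do not bring the early leavers' scores into the means compared with 1.6.

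**Conclusion.** The concern holds as a conditional one. Read as written, the durability model discards the Week 2-6 scores of FAS subjects with no MADRS from Day 49. Its estimates can then be biased, in a direction not known in advance, if dropout depends on post-baseline MADRS. Under the assumptions above the bias is about 0.1 point with equal dependence in both arms and 0.2-0.4 with a twofold difference in slope. It is smaller at lower dropout and larger only in one-arm extremes. A change of up to 14 percentage points in the chance of passing 1.6 (41% against 55%) is enough to matter for a durability claim.

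The Week 6 primary test is untouched, durability carries no alpha, and the interim consequence is small. The change is worth making because it is cheap and uses data already collected.

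**What to change.** In SAP 8.2.1 and IAP 2.2, name the visits: estimate the Week 8 and Week 10 differences from one MMRM with Weeks 2, 4, 6, 8 and 10 as repeated outcomes. Keep the same fixed effects and the unstructured covariance with the planned fallback structures. Do this for MADRS and GAD-7, and align Protocol 9.4.1.2.2. Leave the Week 6 primary analysis as it is. If a joint model was always intended, a sentence saying so is enough.

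Because the joint model reduces MNAR bias without removing it, also state whether the SAP 8.1.3.1 analyses apply to Weeks 8 and 10, and whether the no-withdrawal target extends to those visits.

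The cost is a wording change and one program change, with no new data. The covariance matrix grows from 2×2 to 5×5, with slightly more risk of non-convergence, which the fallbacks cover.
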